The HBV DNA test must be performed for participants who have a negative HBsAg test, a negative HBsAb test, and a positive total HBcAb test.
- Negative hepatitis C virus (HCV) antibody test at screening, or positive HCV antibody test followed by a negative HCV RNA test at screening
The HCV RNA test must be performed for participants who have a positive HCV antibody test.
- If a port for IV delivery is present, acceptance to receive atezolizumab IV, and any other IV medication which may be required, through a peripheral line

Participants with Early-stage NSCLC

- Participants must have a complete resection of a histologically or cytologically confirmed Stage II, IIIA, and selected IIIB (early-stage) NSCLC (per the UICC/AJCC staging system, 8th edition; Brierley et al. 2017)
Accepted types of resection include any of the following: lobectomy, sleeve lobectomy, bilobectomy, or pneumonectomy.
Resection by segmentectomy or wedge resection is not allowed.
If mediastinoscopy was not performed preoperatively, it is expected that, at a minimum, mediastinal lymph node systematic sampling will have occurred. Systematic sampling is defined as removal of at least one representative lymph node at specified levels. For a right thoracotomy, sampling is required at levels 4 and 7 and for a left thoracotomy, levels 5 and/or 6 and 7. Levels 10 and 11 are required irrespective of tumor laterality. Endobronchial ultrasound-guided transbronchial needle aspiration (EBUS-TBNA) is an accepted sampling method.
- PD-L1 expression TC \geq 1% (VENTANA PD-L1 [SP263] IHC assay) or TPS \geq 1% (Dako PD-L1 IHC 22C3 pharmDx assay), as documented through local or central testing of a representative tumor tissue specimen
Participants may be enrolled based on local documentation of PD-L1 expression, if the criteria outlined below are met. If the participant does not have local documentation of PD-L1 expression or local documentation of PD-L1 expression does not meet the defined criteria, central PD-L1 testing is required as outlined below.
Local PD-L1 testing: Documentation of known PD-L1 status, as determined by the VENTANA PD-L1 (SP263) IHC assay or the Dako PD-L1 IHC 22C3 pharmDx assay is required. The PD-L1 assay must be a Health Authority approved test (i.e., adhering to local drug/device regulations) and performed per manufacturer's recommendations and requirements.

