 - Participants with documented liver metastases: AST and ALT $\leq 5 \times$ ULN
 - Participants with documented liver or bone metastases: ALP $\leq 5 \times$ ULN
- Total bilirubin $\leq 1.5 \times$ ULN with the following exception:
 - Participants with known Gilbert disease: total bilirubin $\leq 3 \times$ ULN
- Creatinine clearance ≥ 45 mL/min (calculated through use of the Cockcroft-Gault formula)
- Albumin ≥ 25 g/L (≥ 2.5 g/dL)
- For participants not receiving therapeutic anticoagulation: INR and aPTT $\leq 1.5 \times$ ULN
- For participants receiving therapeutic anticoagulation: stable anticoagulant regimen
- Intact normal skin without potentially obscuring tattoos, pigmentation, or lesions in the area for intended injection
- Negative HIV test at screening, with the following exception: participants with a positive HIV test at screening are eligible provided they are stable on anti-retroviral therapy, have a CD4 count $\geq 200/\mu\text{L}$, and have an undetectable viral load
- Negative hepatitis B surface antigen (HBsAg) test at screening
- Positive hepatitis B surface antibody (HBsAb) test at screening, or negative HBsAb at screening accompanied by either of the following:
 - Negative total hepatitis B core antibody (HBcAb)
 - Positive total HBcAb test followed by a negative (per local laboratory definition) hepatitis B virus (HBV) DNA test
 - The HBV DNA test must be performed for participants who have a negative HBsAg test, a negative HBsAb test, and a positive total HBcAb test.
- Negative hepatitis C virus (HCV) antibody test at screening, or positive HCV antibody test followed by a negative HCV RNA test at screening
 - The HCV RNA test must be performed for participants who have a positive HCV antibody test.
- If a port for IV delivery is present, acceptance to receive atezolizumab IV, and any other IV medication which may be required, through a peripheral line

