Appendix 4: Patient-Reported Outcome Measures

Study Number:	Subject Number:	Visit Name: Cycle  Day 
Site Number:	Date of Assessment:	

THERAPY ADMINISTRATION SATISFACTION QUESTIONNAIRE (TASQ-IV)*

Instructions: Cancer treatment can be given through a port or a thin plastic tube and a needle that was put directly into a vein in your arm, called an intravenous or IV infusion.

Please answer the questions based on your most recent IV infusion.

1. How satisfied or dissatisfied were you with the IV infusion?

Very satisfied Satisfied Neither satisfied nor dissatisfied Dissatisfied Very dissatisfied

2. How much pain did you experience at the IV site?

None Mild Moderate Severe Very Severe

3. How much swelling was there at the IV site?

None Mild Moderate Severe Very Severe

4. How much redness did you experience at the IV site?

None Mild Moderate Severe Very Severe

5. When receiving the IV infusion, do you feel restricted?

Not at all A little bit Somewhat Quite a bit Very much

6. How convenient is it for you to have your IV infusion?

Very convenient Convenient Neither convenient nor inconvenient Inconvenient Very inconvenient

7. How bothered are you by the amount of time it takes to have the infusion?

Not at all bothered A little bothered Moderately bothered Quite bothered Very bothered

8. Does setting up the IV infusion mean you lose or gain time for other things?

Lost a lot of time Lost some time Neither lost nor gained time Gained some time Gained a lot of time

Respondent Initials: _____ Date: _____

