Appendix 5: Healthcare-Professional Reported Outcome Measures

Table 2 Chronological listing of observed tasks

Task	Atezo IV	Atezo SC
Drug preparation area		

 Collection of atezolizumab (includes IV consumables and time to reach aseptic preparation area; and SC vial checks), reconstitution of IV atezolizumab, SC filling, sign-off of prepared IV atezolizumab bags/dispensed SC formulation 	X	X
Treatment room		

 Installation of venous catheter/line flushing 	X	

 Bringing IV bag to patient chair 	X	

 Atezolizumab SC vial check and filling (if not done in drug preparation area) 		X

 Connection of winged infusion set and priming 		X

 Atezolizumab IV infusion initiations 	X	

 Atezolizumab SC administration and immediate monitoring 		X

 Patient monitoring during infusion 	X	

 Disconnecting infusion/flushing line/disposing of materials 	X	

 Disposing of atezolizumab SC vials, winged sets and syringes 		X

 Patient monitoring post-infusion/post-injection (only "active" monitoring time in the treatment room to be collected) 	X	X

¹ Generic task flow is represented, which may deviate from center practice.

² In the drug preparation area, the total time for all tasks combined should be recorded.

³ In all centers, SC injection administration includes immediate monitoring for injection-related reactions.

IV, intravenous; SC, subcutaneous.

This survey will take approximately 5 minutes to complete.

You are being invited to complete this survey because your center is a MO43576 clinical study site.

Questions 1a–1f should be completed for every participant after administration of every cycle during the Treatment Cross-over Period of the study (Cycles 1–6, i.e., 3 cycles of atezolizumab IV followed by 3 cycles of atezolizumab SC or vice versa).

Questions 2–8 should be completed for each participant after administration of study treatment Cycle 6.

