Appendix 5: Healthcare-Professional Reported Outcome Measures

Experience with atezolizumab SC injection and atezolizumab IV infusion administration

Please complete Questions 1a–1f for each patient treatment cycle.

1a. Please indicate which treatment the estimates relate to:

- Atezolizumab SC (proceed to Q1e) Atezolizumab IV (proceed to Q1b)

1b. Did the patient have existing IV access?

- YES (proceed to Q1d) NO (proceed to Q1c)

1c. If new IV access was needed for this cycle of treatment, please indicate what type of IV access was provided and how long (in minutes) this took to set up (atezolizumab IV patients only)?

- central venous catheter
 PICC, peripherally inserted central catheter
 peripheral vein cannulation

..... (please estimate to the nearest minute)

1d. What type of existing IV access did the patient have?

- central venous catheter
 PICC, peripherally inserted central catheter
 peripheral vein cannulation

1e. How long (in minutes) did it take to administer the treatment, i.e., total infusion duration?

..... (please estimate to the nearest minute)

1f. How long (in minutes) was the patient in the Treatment Room for in total?

..... (please estimate to the nearest minute)

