Appendix 5: Healthcare-Professional Reported Outcome Measures

Please indicate any factors during the treatment in the Treatment Room that may have affected the timing estimate (if any):

.....
.....
.....
.....
.....

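### The HCPQ-Treatment Room skip rule at item 1b does not fit the port rule: a port holder's newly placed peripheral line can bypass item 1c, and item 1d can describe access that was not used

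*Protocol*

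**What the plan says.** The inclusion criteria for all participants (Protocol 4.1.1.1, repeated in the synopsis) contain a rule for port holders: "If a port for IV delivery is present, acceptance to receive atezolizumab IV, and any other IV medication which may be required, through a peripheral" vein. The port may be present, but it is not the route for study infusions.

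Protocol Appendix 5, HCPQ-Treatment Room, has items 1a to 1f completed for every participant at every cycle of the Treatment Cross-over Period. On an IV cycle, item 1b asks whether the patient already had IV access, with the routing "YES (proceed to Q1d) NO (proceed to Q1c"). Item 1c begins "If new IV access was needed for this cycle of treatment, please indicate what type of IV access was provided and how long" it took to set up. Item 1d asks "What type of existing IV access did the patient have" and offers central venous catheter, PICC or peripheral cannulation. Item 1e is the infusion duration and 1f the total time in the Treatment Room. A free-text item follows: "Please indicate any factors during the treatment in the Treatment Room that may have affected the timing estimate". Table 2 of the same appendix lists "Installation of venous catheter/line flushing" among the Treatment Room tasks for IV.

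Healthcare professionals' perception of time and resource use is a secondary objective, reported by individual question (Protocol 2.2). SAP 4.2.9 summarises the Treatment Room experience items by cycle and by route, on the FAS.

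**The concern.** The form takes existing access to be the access that is used. For most patients that is reasonable. For a port holder the protocol itself makes it untrue: there is existing access, and a different line has to carry the dose.

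Protocol 3.3.5 says the HCPQs are meant to show whether shorter SC administration, together with SC not needing venous access, leads to favourable perceptions of resource use. Placing a line is thus part of the IV burden that the form is meant to describe. If the skip rule removes some placements from 1c, that item under-counts new lines on IV cycles, and its set-up minutes come from an incomplete set of infusions. Item 1d, in turn, would report access types that played no part in giving the drug.

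**Working it through.** The plan states no figure on this point, so the check is a trace of the form against the eligibility rule. Take a port holder on an IV cycle for whom a peripheral line is newly placed.

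| Item | Literal reading (YES at 1b) | Second reading (NO at 1b) |
|---|---|---|
| 1b | The port counts as existing access | The port does not count, as it cannot be used for this dose |
| 1c: type and set-up minutes of new line | Not reached | Completed |
| 1d: type of existing access | Asked; no port option, and the line used is not asked | Nothing to describe |
| 1e: infusion duration | Completed | Completed |
| 1f: total room time | Completed; includes placement done in the room | Same |
| Free text | Available | Available |

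Three things follow.

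1. Under the literal reading no structured item holds the set-up minutes. Item 1e covers the infusion only. Item 1f includes placement done in the room but does not separate it.
2. Under the literal reading 1d has no correct answer for a port. A site might leave it blank, tick central venous catheter as the nearest option, or tick peripheral cannulation for the line it has just placed. Only the last describes the line used, and it does so under the label of existing access.
3. The form does not say which reading is meant. With 40 to 50 sites planned (Protocol 3.1.1), the same infusion can appear as existing access without set-up time at one site and as new access with set-up time at another.

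Size. Let f be the share of IV infusions in which a port holder has a new line placed, and r the share of those forms filled in literally. Then

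share of IV Treatment Room forms that wrongly lack 1c = f × r,

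which is 0 when r = 0 and f when r = 1. The documents give neither f nor r. Per person, the cross-over period has three IV cycles, so one port holder contributes at most three such forms.

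Direction. Missing 1c entries lower the count of new placements on IV cycles. Whether the average set-up time moves up or down cannot be said, because the documents do not indicate whether cannulation takes longer or shorter in port holders.

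**The case against.** The best defence is that the second reading is the natural one. Item 1c is conditional on new access being needed for the cycle, which is exactly the port holder's situation. The lack of a port option at 1d also suits a form about access usable for this drug. The form is on paper (Protocol 4.5.8), so nothing prevents a site from completing 1c. Under that reading no form is affected. This stands as a possible reading, but it conflicts with the printed arrows, and nothing in the form or the SAP settles the matter.

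It is also fair that the time is not lost. Line installation is a listed task, 1f can contain it, and the free text can explain it. This stands and limits the point to separate recording.

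Stronger readings are tempting, and the documents do not support them.

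- A reader might infer that the port rule biases the primary SC-preference proportion, and ask for a result without port holders or a reworded estimand. The documents give neither port prevalence nor any preference difference by port status, and the primary analysis has no hypothesis test (SAP 2.1). There is no basis for either request.
- A reader might conclude that port status is recorded nowhere. The full eCRF is not among the documents, surgeries and prior cancer procedures are collected at baseline (Protocol 4.5.2), and sites must establish port presence to apply the criterion.
- A reader might count affected forms by taking the 126 participants of the sample-size section at three IV infusions each. That number is the precision target for preference. The HCPQs are analysed on the FAS, which is all randomized participants (about 175 planned), and not everyone will have three IV doses.

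**Conclusion.** The routing at 1b is inconsistent with the port rule. Followed as printed, it leaves the type and set-up time of a port holder's newly placed peripheral line without a separate record, and it makes 1d describe access that was not used. Because a second reading is open to sites, coding may also differ between them.

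The consequence is confined to the 1c and 1d summaries within one descriptive secondary endpoint. Total room time is unaffected. The size is unknown: it lies between zero and the share of IV infusions in which a port holder has a new line placed, and the documents do not give that share. The conclusion assumes only that some port holders are enrolled and that at least some sites follow the printed arrows. It is a minor point. It does not touch the primary preference proportion, and the eligibility criterion itself is not in question.

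**What to change.** Leave the inclusion criterion as it is and correct the form in one of two ways:

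- reword 1b to *Was existing IV access used for this infusion?*, keeping the present arrows; or
- keep 1b and require 1c whenever a new line is placed for the infusion, whatever other access the patient has.

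In either case, limit 1d to the existing access used for that infusion. No new analysis, subgroup or change to the estimand is needed.

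The cost is a wording or routing change on one paper form, with its translations where these exist, and a short note to sites. Forms completed before the change keep the old routing. When 1c and 1d are reported, the text should say so and state that, on those forms, 1c may omit lines placed in port holders and 1d may describe access that was not used.

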4.1.1.2 Participants with Early-stage NSCLC

- Participants must have a complete resection of a histologically or cytologically confirmed Stage II, IIIA, and selected IIIB (early-stage) NSCLC (per the UICC/AJCC staging system, 8th edition; Brierley et al. 2017)

Accepted types of resection include any of the following: lobectomy, sleeve lobectomy, bilobectomy, or pneumonectomy.

Resection by segmentectomy or wedge resection is not allowed.

If mediastinoscopy was not performed preoperatively, it is expected that, at a minimum, mediastinal lymph node systematic sampling will have occurred. Systematic sampling is defined as removal of at least one representative lymph node at specified levels. For a right thoracotomy, sampling is required at levels 4 and 7 and for a left thoracotomy, levels 5 and/or 6 and 7. Levels 10 and 11 are required irrespective of tumor laterality. Endobronchial ultrasound-guided transbronchial needle aspiration (EBUS-TBNA) is an accepted sampling method.

- PD-L1 expression TC \geq 1% (VENTANA PD-L1 [SP263] IHC assay) or TPS \geq 1% (Dako PD-L1 IHC 22C3 pharmDx assay), as documented through local or central testing of a representative tumor tissue specimen

Participants may be enrolled based on local documentation of PD-L1 expression, if the criteria outlined below are met. If the participant does not have local documentation of PD-L1 expression or local documentation of PD-L1 expression does not meet the defined criteria, central PD-L1 testing is required as outlined below and in Section 4.5.6.

Local PD-L1 testing: Documentation of known PD-L1 status, as determined by the VENTANA PD-L1 (SP263) IHC assay or the Dako PD-L1 IHC 22C3 pharmDx assay is required. The PD-L1 assay must be a Health Authority approved test (i.e., adhering to local drug/device regulations) and performed per manufacturer's recommendations and requirements.

Central PD-L1 testing: When central testing is required, a formalin-fixed, paraffin-embedded (FFPE) tumor specimen (archival or fresh) in a paraffin block (preferred) or at least 5 serial slides containing unstained, freshly cut, serial sections must be submitted along with an associated pathology report prior to study enrollment. Refer to Section 4.5.6 for additional information on tumor specimens collected at prescreening/screening.

- Participants must have completed adjuvant chemotherapy at least 4 weeks and up to 12 weeks prior to randomization and must be adequately recovered from chemotherapy. For patients in the adjuvant setting, neoadjuvant chemotherapy or chemoradiotherapy is acceptable provided that patients also received adjuvant chemotherapy as per protocol's requirement.

4.1.1.3 Participants with Stage IV NSCLC

- Histologically or cytologically confirmed, Stage IV non-squamous or squamous NSCLC (per the UICC/AJCC staging system, 8th edition; Brierley et al. 2017)

Participants with tumors of mixed histology must be classified as non-squamous or squamous based on the major histological component.

- Life expectancy \geq 18 weeks in the opinion of the investigator

- PD-L1 expression TC \geq 50% (VENTANA PD-L1 (SP263) IHC assay) or TPS \geq 50% (Dako PD-L1 IHC 22C3 pharmDx assay), or TC3 or IC3 (VENTANA PD-L1 (SP142) IHC assay), as documented through local or central testing of a representative tumor tissue specimen.

Participants may be enrolled based on local documentation of PD-L1 expression, if the criteria outlined below are met. If the participant does not have local documentation of PD-L1 expression or local documentation of PD-L1 expression does not meet the defined criteria, central PD-L1 testing is required as outlined below and in Section 4.5.6.

Local PD-L1 testing: Documentation of known PD-L1 status as determined by the VENTANA PD-L1 (SP263) IHC assay, Dako PD-L1 IHC 22C3 pharmDx assay or VENTANA PD-L1 (SP142) IHC assay is required. The PD-L1 assay must be a Health Authority approved test (i.e., adhering to local drug/device regulations) and performed per manufacturer's recommendations and requirements.

Central PD-L1 testing: When central testing is required, a formalin-fixed, paraffin-embedded (FFPE) tumor specimen (archival or fresh) in a paraffin block (preferred) or at least 5 serial slides containing unstained, freshly cut, serial sections must be submitted along with an associated pathology report prior to study enrollment. Refer to Section 4.5.6 for additional information on tumor specimens collected at screening.

- No prior systemic treatment for Stage IV non-squamous or squamous NSCLC
- Participants who have received prior neo-adjuvant, adjuvant chemotherapy, radiotherapy, or chemoradiotherapy with curative intent for non-metastatic disease must have experienced a treatment-free interval of at least 6 months from randomization since the last chemotherapy, radiotherapy, or chemoradiotherapy cycle.

4.1.2 Exclusion Criteria

Participants who meet any of the following criteria will be excluded from study entry:

4.1.2.1 All Participants

- History of malignancy within 5 years prior to initiation of study treatment, with the exception of the cancer under investigation in this study and malignancies with a negligible risk of metastasis or death (e.g., 5-year OS rate $>$ 90%), such as adequately treated carcinoma in situ of the cervix, non-melanoma skin carcinoma, localized prostate cancer, ductal carcinoma in situ, or Stage I uterine cancer

- Uncontrolled tumor-related pain

Participants requiring pain medication must be on a stable regimen at study entry.

Symptomatic lesions (e.g., bone metastases or metastases causing nerve impingement) amenable to palliative radiotherapy should be treated prior to enrollment. Participants should be recovered from the effects of radiation. There is no required minimum recovery period.

Asymptomatic metastatic lesions that would likely cause functional deficits or intractable pain with further growth (e.g., epidural metastasis that is not currently associated with spinal cord compression) should be considered for loco-regional therapy, if appropriate, prior to enrollment.

- Uncontrolled pleural effusion, pericardial effusion, or ascites requiring recurrent drainage procedures (once monthly or more frequently)

Participants with indwelling catheters (e.g., PleurX[®]) are allowed.

- Participants known to have a sensitizing mutation in the EGFR gene or an ALK fusion oncogene

Participants with unknown EGFR or ALK mutational status who may harbor a sensitizing EGFR mutation (i.e., participants with non-squamous histology (including those with a mixed histology that includes any non-squamous component), and without any other known driver mutation) will be required to be tested at prescreening/screening. Participants with tumors of squamous histology who have an unknown EGFR or ALK mutational status will not be required to be tested at prescreening/screening.

EGFR and/or ALK may be assessed locally or at a central laboratory. EGFR status assessed locally must be performed on tissue using a test that detects mutations in exons 18–21. The assays must be a Health Authority approved test (i.e., adhering to local drug/device regulations) and performed per manufacturer's recommendations and requirements. If the assay does not meet the criteria above, EGFR and/or ALK must be assessed centrally. If samples are submitted for central EGFR and/or ALK testing, additional slides must be provided (see laboratory manual) along with an associated pathology report prior to study enrollment.

- History of leptomeningeal disease
- Uncontrolled or symptomatic hypercalcemia (ionized calcium > 1.5 mmol/L, calcium > 12 mg/dL, or corrected calcium greater than ULN)

- Active or history of autoimmune disease or immune deficiency, including, but not limited to, myasthenia gravis, myositis, autoimmune hepatitis, systemic lupus erythematosus, rheumatoid arthritis, inflammatory bowel disease, anti-phospholipid antibody syndrome, granulomatosis with polyangiitis, Sjögren syndrome, Guillain-Barré syndrome, or multiple sclerosis (see [Appendix 7](#) for a more comprehensive list of autoimmune diseases and immune deficiencies), with the following exceptions:

Participants with a history of autoimmune-related hypothyroidism who are on thyroid-replacement hormone are eligible for the study.

Participants with controlled Type 1 diabetes mellitus who are on an insulin regimen are eligible for the study.

Participants with eczema, psoriasis, lichen simplex chronicus, or vitiligo with dermatologic manifestations only (e.g., participants with psoriatic arthritis are excluded) are eligible for the study provided all of following conditions are met:

- Rash must cover < 10% of body surface area.
- Disease is well controlled at baseline and requires only low-potency topical corticosteroids.
- There has been no occurrence of acute exacerbations of the underlying condition requiring psoralen plus ultraviolet A radiation, methotrexate, retinoids, biologic agents, oral calcineurin inhibitors, or high-potency or oral corticosteroids within the previous 12 months.

- History of idiopathic pulmonary fibrosis, organizing pneumonia (e.g., bronchiolitis obliterans), drug-induced pneumonitis, or idiopathic pneumonitis, or evidence of active pneumonitis on screening chest computed tomography (CT) scan

History of radiation pneumonitis in the radiation field (fibrosis) is permitted.

- Active tuberculosis
- Significant cardiovascular disease (such as New York Heart Association Class II or greater cardiac disease, myocardial infarction, or cerebrovascular accident) within 3 months prior to initiation of study treatment, unstable arrhythmia, or unstable angina
- Major surgical procedure, other than for diagnosis, within 4 weeks prior to initiation of study treatment, or anticipation of need for a major surgical procedure during the study
- Severe infection within 4 weeks prior to initiation of study treatment, including, but not limited to, hospitalization for complications of infection, bacteremia, or severe pneumonia, or any active infection that could impact participant safety
- Treatment with therapeutic oral or IV antibiotics within 2 weeks prior to initiation of study treatment

Participants receiving prophylactic antibiotics (e.g., to prevent a urinary tract infection or chronic obstructive pulmonary disease (COPD) exacerbation) are eligible for the study.

- Prior allogeneic stem cell or solid organ transplantation
- Any other disease, metabolic dysfunction, physical examination finding, or clinical laboratory finding that contraindicates the use of an investigational drug, may affect the interpretation of the results, or may render the participant at high risk from treatment complications
- Treatment with a live, attenuated vaccine within 4 weeks prior to initiation of study treatment, or anticipation of need for such a vaccine during atezolizumab treatment or within 5 months after the final dose of atezolizumab
- Current treatment with anti-viral therapy for HBV
- Treatment with investigational therapy within 28 days prior to initiation of study treatment
- Prior treatment with CD137 agonists or immune checkpoint blockade therapies, including anti-PD-1 and anti-PD-L1 therapeutic antibodies
 - Participants who have had prior anti-CTLA-4 treatment may be enrolled, provided the following requirements are met:
 - Last dose of anti-CTLA-4 at least 6 weeks prior to randomization
 - No history of severe immune-mediated adverse effects from anti-CTLA-4 (NCI CTCAE Grades 3 and 4)
- Treatment with systemic immunostimulatory agents (including, but not limited to, interferon and IL-2) within 4 weeks or 5 drug-elimination half-lives (whichever is longer) prior to initiation of study treatment
 - Prior treatment with cancer vaccines is allowed.
- Treatment with systemic immunosuppressive medication (including, but not limited to, corticosteroids, cyclophosphamide, azathioprine, methotrexate, thalidomide, and anti-tumor necrosis factor- α [TNF- α] agents) within 2 weeks prior to initiation of study treatment, or anticipation of need for systemic immunosuppressive medication during study treatment, with the following exceptions:
 - Participants who received acute, low-dose systemic immunosuppressant medication or a one-time pulse dose of systemic immunosuppressant medication (e.g., 48 hours of corticosteroids for a contrast allergy) are eligible for the study.
 - Participants who received mineralocorticoids (e.g., fludrocortisone), inhaled or low-dose corticosteroids for COPD or asthma, or low-dose corticosteroids for orthostatic hypotension or adrenal insufficiency are eligible for the study.
- History of severe allergic anaphylactic reactions to chimeric or humanized antibodies or fusion proteins
- Known hypersensitivity to Chinese hamster ovary cell products or to any component of the atezolizumab formulation

- Pregnancy or breastfeeding, or intention of becoming pregnant during study treatment or 5 months after the final dose of study treatment
 - Women of childbearing potential must have a negative serum pregnancy test result within 14 days prior to initiation of study treatment.
- Known allergy or hypersensitivity to hyaluronidase, bee or vespid venom, or any other ingredient in the formulation of rHuPH20
- Pathology (e.g., lower extremity edema, cellulitis, lymphatic disorder or prior surgery, preexisting pain syndrome, previous lymph node dissection, etc.) that could interfere with any protocol-specified outcome assessment (e.g., PK)
- Spinal cord compression not definitively treated with surgery and/or radiation, or previously diagnosed and treated spinal cord compression without evidence that disease has been clinically stable for ≥ 2 weeks prior to randomization

